FOP	Fibrodysplasia Ossificans Progressiva
FOP-PFQ	FOP-Physical Function Questionnaire
FPS-R	Faces Pain Scale-Revised
HO	heterotopic ossification
MedDRA	Medical Dictionary for Regulatory Activities
MRI	magnetic resonance imaging
NRS	numeric rating scales
PCS	potentially clinically significant
PROMIS	Patient-Reported Outcomes Measurement Information System
RAR γ	retinoic acid receptor gamma
ROM	range of motion
SAE	serious adverse event
SAP	statistical analysis plan
ULN	upper limit of normal
US	ultrasound

1 Introduction

This Statistical Analysis Plan (SAP) describes the detailed analyses to be performed for Study PVO-1A-202 Part A. These analyses are based on Amendment 2 of the protocol dated 22 June 2015 and Amendment 3 of the protocol dated 10 March 2016. The analyses to be performed for Study PVO-1A-202 Part B will be described in a separate SAP. Note that analyses related to the Follow-up Component objectives as described in [Section 2.1](#) will be addressed in the Part B SAP.

2 Overview

2.1 Study Objectives

2.1.1 Primary Objective

The primary objectives are:

- To evaluate the long-term safety and efficacy of prior palovarotene treatment in FOP subjects who completed Study PVO-1A-201 (**Follow-up Component**; up to 12 months).
- To evaluate the safety and efficacy of palovarotene in FOP subjects experiencing up to two, new, distinct flare-ups (**Flare-up Component**; up to 36 months). Efficacy will be based on the ability of palovarotene to prevent heterotopic ossification (HO) at the new, distinct flare-up site as assessed by low-dose computed tomography (CT) scan (or plain radiographs for subjects unable to undergo CT scan).

2.1.2 Secondary Objectives

The secondary objectives for the **Follow-up Component** are:

- To evaluate the amount of HO at the original flare-up site by plain radiograph.
- To evaluate active range of motion (ROM) by goniometer at the original flare-up site.
- To evaluate ROM as assessed by the Cumulative Analogue Joint Involvement Scale for FOP (CAJIS).
- To evaluate the subject and Investigator global assessment of movement at the original flare-up site.
- To evaluate pain and swelling at the original flare-up site using numeric rating scales (NRS) or the Faces Pain Scale-Revised (FPS-R) in subjects under 8 years of age.
- To evaluate physical function using age-appropriate forms of the FOP-Physical Function Questionnaire (FOP-PFQ).
- To evaluate physical and mental health using age-appropriate forms of the Patient Reported Outcomes Measurement Information System (PROMIS) Global Health Scale.
- To evaluate the use of assistive devices and adaptations for daily living by FOP subjects.
- To evaluate bone, cartilage, angiogenesis, and inflammation biomarkers; and explore correlations between changes from baseline in biomarkers and clinical efficacy.

The secondary objectives for the **Flare-up Component** are:

- To evaluate the effect of palovarotene on active ROM at the new, distinct flare-up site as assessed by goniometer.

- To evaluate the effect of palovarotene on ROM as assessed by CAJIS.
- To evaluate the effect of palovarotene by the subject and Investigator global assessment of movement at the new, distinct flare-up site.
- To evaluate the effect of palovarotene on physical function using age-appropriate forms of the FOP-PFQ.
- To evaluate the effect of palovarotene on physical and mental health using age-appropriate forms of the PROMIS Global Health Scale.
- To evaluate the effect of palovarotene on the use of assistive devices and adaptations for daily living by FOP subjects.
- To evaluate the effects of palovarotene on soft tissue swelling and cartilage formation at the new, distinct flare-up site as assessed by magnetic resonance imaging (MRI); or the effect of palovarotene on soft tissue swelling as assessed by ultrasound (US) in subjects unable to undergo MRI.
- To evaluate bone, cartilage, angiogenesis, and inflammation biomarkers; and explore correlations between changes from baseline in biomarkers and clinical efficacy.

2.2 Study Population

Approximately 40 subjects who completed Study PVO-1A-201 will be enrolled in Study PVO-1A-202 Part A.

2.3 Study Design

Study PVO-1A-202 Part A is a Phase 2, multicenter, event-based, open-label extension of Study PVO-1A-201. This open-label extension will give subjects who completed Study PVO-1A-201 the opportunity to be followed for up to an additional 36 months, and receive open-label palovarotene should they experience up to two, new, distinct flare-ups.

All enrolled subjects will participate in the **Follow-up Component** of the study. The Follow-up Component will include visits at Study Screening and Study Months 6, 12, 18, 24, 30, and 36. Study Day 1 will be the date of informed consent. Visit windows are +/- 2 weeks. Assessments related to flare-ups during the Follow-up Component will be evaluated at the original flare-up site from Study PVO-1A-201.

Subjects who experience an eligible flare-up will participate in the **Flare-up Component** of the study. The Flare-up Component will include visits at Flare-up Screening and Flare-up Weeks 2, 4, 6, 9, and 12. Flare-up Day 1 will be the date of first dose of study drug for the flare-up. Visit windows are +/- 3 days. Assessments related to flare-ups during the Flare-up Component will be evaluated at new flare-up sites from Study PVO-1A-202 Part A. Note that subjects may have more than one unique new flare-up and that each flare-up will be assessed and analyzed independently.

2.4 Study Treatment

Subjects who experience an eligible flare-up will receive palovarotene 10 mg for 14 days followed by palovarotene 5 mg for 28 days or exposure equivalent doses based on subject

weight. Weight-adjusted doses of palovarotene estimated to achieve exposures equivalent to 10 mg and 5 mg are:

Weight Range Category	10-mg Equivalent	5-mg Equivalent	2.5-mg Equivalent *
20 to <40 kg	6 mg	3 mg	1.5 mg
40 to <60 kg	8 mg	4 mg	2 mg
≥60 kg	10 mg	5 mg	2.5 mg

* In the event of dose de-escalation.

In the event the subject requires dose de-escalation due to an intolerable side effect in Study PVO-1A-201, then the dose the subject will receive for a subsequent flare-up will be determined by the Investigator and the Medical Monitor. Dose reduction to one half of the palovarotene dose may also occur should the subject experience an adverse event that may otherwise result in study drug discontinuation; if a subject is already receiving the lowest possible dose, then study drug will be discontinued.

Subjects who do not experience an eligible flare-up will not be treated.

2.5 Randomization and Blinding

This is an open-label study and does not involve randomization or blinding.

3 General

Categorical data will be summarized with counts and percentages. Percentages will be calculated based on the number of non-missing values and will be reported to one decimal place.

Continuous data will be summarized with descriptive statistics including the number of non-missing values, mean, standard deviation, standard error, median, minimum, and maximum. Minimum and maximum will be reported to the same precision as the raw values, mean and median will be reported to one additional decimal place, and standard deviation and standard error will be reported to two additional decimal places. Some discretion may be applied.

All data will be listed. When listings will be provided instead of summaries or require additional description, they are described in this document.

3.1 Adjustments for Covariates

Baseline covariates may be added to statistical models as the data allow. The sample size of this study may preclude the inclusion of covariate effects in some instances.

3.2 Handling of Dropouts or Missing Data

As there is no effective treatment for these subjects, it is assumed they will be highly motivated to adhere to the protocol and treatment visits. Thus, it is expected that there will be limited missing data, and most subjects will complete the study. The primary analysis will be performed using observed data only. Missing data will not be replaced.

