4.4 Efficacy Population

The Efficacy Population will include all subjects in the Treated Population who had an evaluable Week 6 or Week 12 image (CT scan or x-ray). Analyses based on the Efficacy Population will generally be summarized in total. Note that data collected for flare-ups may use each flare-up as the unit of analysis rather than each subject. The Efficacy Population will be the primary population for analysis of efficacy assessments performed at Flare-up Component visits.

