7.1 Primary Efficacy

CT scan (or x-ray for subjects unable to undergo CT scan) will be performed at:

- Screening/Baseline, Week 6, and Week 12 (Flare-up Component).

The primary efficacy analysis is the proportion of flare-ups with no new HO at Week 12 as assessed by CT scan (or by x-ray for subjects unable to undergo CT scan). Note that “no new HO at Week 12” means no new HO at Week 12 compared to baseline.

The presence of HO at baseline and the incidence of no new HO and new HO at post-baseline visits will be summarized with counts and percentages of flare-ups.

Similar analyses will be performed for subgroups defined by baseline edema severity (no edema, any edema, mild edema, moderate edema, severe edema, and moderate or severe edema [higher-intensity flare-ups]). See [Section 7.2.4](#) for a description of edema determination.

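### Part A: the primary Week 12 proportion leaves out flare-ups that have a Week 6 scan but no evaluable Week 12 scan, so it is unbiased only if Week 12 missingness is unrelated to the Week 6 result

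*SAP*

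**What the plan says.** All references are to the Part A SAP.

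- **Population (section 4.4).** The Efficacy Population is "all subjects in the Treated Population who had an evaluable Week 6 or Week 12 image (CT scan or x-ray". It is the primary population for efficacy at Flare-up Component visits. It is defined by subject, although "data collected for flare-ups may use each flare-up as the unit of analysis rather than each subject".
- **Primary analysis (section 7.1).** "The primary efficacy analysis is the proportion of flare-ups with no new HO at Week 12 as assessed by CT scan", or by x-ray where CT is not possible. The section adds that this "means no new HO at Week 12 compared to baseline". Scans are scheduled at baseline, Week 6 and Week 12, and new HO is also tabulated at post-baseline visits.
- **Missing data (section 3.2).** "The primary analysis will be performed using observed data only. Missing data will not be replaced".
- **Denominator (section 3, General).** "Percentages will be calculated based on the number of non-missing values".

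No part of the Part A SAP says how a flare-up with a Week 6 result and no Week 12 result enters the primary proportion. No sensitivity analysis is planned for a missing Week 12 scan.

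**The concern.** The rule for entering the population and the rule for entering the primary proportion do not select the same flare-ups. A Week 6 scan is enough for the first; only a Week 12 scan is enough for the second. The flare-ups in the gap are not uninformative, because each has a reading of the outcome of interest, in the same flare-up, six weeks before the primary time point.

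Two things are at stake. First, the observed-only proportion is a fair estimate for the Efficacy Population only if losing the Week 12 scan has nothing to do with what the Week 6 scan showed. The SAP neither states nor checks this. Second, Part A enrols about 40 subjects and treats only those with an eligible flare-up, so a few flare-ups can move the headline figure by several points. The planned edema subgroups use the same rule with smaller denominators.

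**Working it through.** The Part A SAP states no expected rate, dropout rate or number of treated flare-ups, so there is no figure of its own to reproduce. All rates and counts below are assumptions chosen to show direction and range. 'Clear' means no new HO compared with baseline.

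**Step 1. Who is counted.**

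| Week 6 scan | Week 12 scan | Qualifies for Efficacy Population | In primary proportion |
|---|---|---|---|
| new HO | read | yes | yes, by its Week 12 result |
| clear | read | yes | yes, by its Week 12 result |
| missing | read | yes | yes, by its Week 12 result |
| new HO | missing | yes | no |
| clear | missing | yes | no |

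The last two rows are the gap, and both kinds of case fall into it.

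**Step 2. Bias formula.** Suppose every flare-up has a Week 6 scan. Let

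- h6 = P(new HO at Week 6)
- h12 = P(new HO at Week 12, given clear at Week 6)
- r = P(clear at Week 12, given new HO at Week 6)
- m0 and m1 = P(Week 12 missing) after a clear Week 6 and after new HO at Week 6

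Target: T = (1−h6)(1−h12) + h6·r

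Observed-only: O = [(1−h6)(1−m0)(1−h12) + h6(1−m1)r] / [(1−h6)(1−m0) + h6(1−m1)]

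The difference is O − T = [w − (1−h6)] × (1−h12−r), where w = (1−h6)(1−m0) / [(1−h6)(1−m0) + h6(1−m1)]. If m0 = m1, then w = 1−h6 and the bias is zero. If m1 > m0 the bias is upward, and if m1 < m0 it is downward, provided r is below 1−h12. Any r above zero makes it smaller, so the figures below, with r = 0, are the largest for these inputs.

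**Step 3. Numbers.** Take h6 = 0.30, h12 = 0.10, r = 0, so T = 0.70 × 0.90 = 63.0%. With m0 = 0.05 the numerator of O is 0.70 × 0.95 × 0.90 = 0.5985.

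| m1 | Denominator | O | O − T (points) |
|---|---|---|---|
| 0.05 (equal) | 0.665 + 0.285 = 0.950 | 63.0% | 0 |
| 0.10 | 0.665 + 0.270 = 0.935 | 64.0% | +1.0 |
| 0.20 | 0.665 + 0.240 = 0.905 | 66.1% | +3.1 |
| 0.30 | 0.665 + 0.210 = 0.875 | 68.4% | +5.4 |
| 0.40 | 0.665 + 0.180 = 0.845 | 70.8% | +7.8 |

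Reverse pattern, m0 = 0.10 and m1 = 0.05: O = 0.567/0.915 = 62.0%, which is 1.0 point too low.

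Varying h6 from 0.20 to 0.40, with m1 from 0.10 to 0.40 and m0 = 0.05:

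- smallest: h6 = 0.20, m1 = 0.10, 0.684/0.940 = 72.8% against 72.0%, +0.8 points
- largest: h6 = 0.40, m1 = 0.40, 0.513/0.810 = 63.3% against 54.0%, +9.3 points

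**Step 4. The same in counts.** Assume 30 flare-ups, 9 of which would show new HO at Week 12, so complete data give 21/30 = 70.0%.

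- Two Week 12 scans missing, both after new HO at Week 6: 21/28 = 75.0%.
- Three missing, one after new HO and two after a clear scan that would have stayed clear: 19/27 = 70.4%. The losses nearly cancel.
- In that second case, counting only the Week 6 new HO case as a failure gives 19/28 = 67.9%, below the complete-data 70.0%. A one-sided failure rule therefore cannot replace an estimate that handles both kinds of missing case.

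**Step 5. An estimate that uses Week 6.** Weight the conditional Week 12 probabilities by the Week 6 distribution: P(clear at W6) × P(clear at W12 | clear at W6) + P(new HO at W6) × P(clear at W12 | new HO at W6). With the Step 3 inputs this is 0.70 × 0.90 + 0.30 × 0 = 63.0% for every m0 and m1, because missingness that depends only on the Week 6 result leaves the conditional probabilities unchanged.

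**The case against.** The strongest reply is that the plan is explicit and coherent. The Efficacy Population serves all Flare-up Component efficacy summaries, including those at Week 6, so admitting subjects on either image is sensible and does not contradict section 7.1. Week 6 new HO is tabulated by visit in section 7.1, and all data are listed. Part A is open-label and section 7.1 plans only counts and percentages, so a reader can see the Week 6 cases. Section 3.2 expects little missing data, and the number of affected flare-ups may be zero. All of this stands. It limits the importance of the point, but it does not supply a rule for the primary proportion.

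A reader might infer three stronger things that the document does not support:

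- **That the primary proportion is necessarily inflated.** Clear flare-ups without a Week 12 scan are dropped too. Nothing in the SAP shows that scans are lost more often after Week 6 new HO, and Step 3 gives zero bias with equal missingness and a downward bias in the reverse case.
- **That the Week 6 finding is thrown away.** It is absent only from the primary proportion. It remains in the by-visit table and in the secondary subgroups defined by new HO at any post-baseline visit (sections 7.2.1 and 7.2.5).
- **That every Week 6 new HO is an established failure and should be counted as one.** This would change the endpoint from Week 12 to any time up to Week 12, and would overrule a Week 12 scan read as clear. Persistence is not guaranteed. The grades in section 7.2.1 include fluid attenuation and calcification without bone formation, the volume rule there allows for a lesion smaller than at baseline, and section 7 acknowledges variability from reading each time point separately.

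**Conclusion.** The point holds in a limited form. Under sections 3, 3.2, 4.4 and 7.1 read together, a flare-up with a Week 6 result and no evaluable Week 12 scan can be in the primary population but in neither the numerator nor the denominator of the primary proportion. That proportion is unbiased for the Efficacy Population only if Week 12 missingness is unrelated to the Week 6 result. The direction of any bias is not known from the SAP.

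The size is also unknown. The range of about 1 to 9 points (0.8 to 9.3) assumes 20% to 40% new HO at Week 6, a further 10% of clear flare-ups converting by Week 12, no reversal of Week 6 new HO, and Week 12 missing in 10% to 40% after new HO against 5% after a clear scan. With limited missing data, as the SAP expects, the effect may be small or nil. The case for a change is that scans already collected can remove a dependence on an unstated assumption at almost no cost, not that the planned result is shown to be wrong.

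**What to change.** Keep the endpoint at Week 12 and amend sections 3.2 and 7.1 as follows.

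1. **Add an estimate that uses the Week 6 result for flare-ups missing Week 12**, by the formula in Step 5. Take the Week 6 probabilities from all flare-ups with a Week 6 scan and the conditional probabilities from those with both scans. Flare-ups with only a Week 12 scan enter through the likelihood.
2. **Add a sensitivity analysis** that counts new HO at Week 6 with a missing Week 12 scan as new HO.
3. **Show the observed-only Week 12 proportion alongside**, with the number of missing Week 12 scans by Week 6 result, so that the reader can judge the missingness directly.
4. **State the scan requirement per flare-up.** Because the population is defined by subject, a second flare-up with no post-baseline scan could otherwise enter through the first.

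The cost is SAP wording and a few lines of code, with no new visits, scans or data. The drawbacks are that the estimate assumes Week 12 missingness depends only on the Week 6 result, that the conditional probabilities (especially after new HO at Week 6) rest on few flare-ups, and that the reported proportion may be slightly less favourable.

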3.3 Interim Analyses

No interim analysis is planned.

3.4 Multicenter Studies

A review of by-center effects will be performed in the context of data listing review. However, the sample size precludes formal assessment of by-center effects.

3.5 Multiple Comparison/Multiplicity

As this is an extension of an initial proof-of-concept study, no correction for multiple testing is planned.

3.6 Examination of Subgroups

The sample size in this study is not sufficient to allow for rigorous assessment of outcomes by subgroups, and the study is not powered for subgroup assessment. However, exploratory assessments of the outcomes may be performed by a number of extrinsic or intrinsic factors, including age of the subject, location of the flare-up, number of flare-up treatments, or other variables as appropriate.

3.7 Study Day and Flare-up Study Day

Study Day will be determined from the date of informed consent (Study Day 1); Study Day -1 will be the day immediately prior to Study Day 1.

Flare-up Study Day will be determined from the date of first dose of a treated flare-up (Flare-up Study Day 1); Flare-up Study Day -1 will be the day immediately prior to Flare-up Study Day 1.

4 Analysis Populations

There will be five populations defined for the analysis.

4.1 Enrolled Population

The Enrolled Population will include all subjects enrolled in Study PVO-1A-202 Part A. Analyses based on the Enrolled Population will generally be summarized by treatment (Untreated, Palovarotene 10 mg/5 mg) and in total. The Enrolled Population will be the primary population for demographic and baseline summaries and for the analysis of adverse events.

4.2 Untreated Population

The Untreated Population will include all subjects who did not take any palovarotene in Study PVO-1A-202 Part A.

4.3 Treated Population

The Treated Population will include all subjects who took at least one dose of palovarotene in Study PVO-1A-202 Part A. Analyses based on the Treated Population will generally be summarized in total. Note that data collected for flare-ups may use each flare-up as the unit of

analysis rather than each subject. The Treated Population will be the primary population for analysis of safety assessments performed at Flare-up Component visits.

4.4 Efficacy Population

The Efficacy Population will include all subjects in the Treated Population who had an evaluable Week 6 or Week 12 image (CT scan or x-ray). Analyses based on the Efficacy Population will generally be summarized in total. Note that data collected for flare-ups may use each flare-up as the unit of analysis rather than each subject. The Efficacy Population will be the primary population for analysis of efficacy assessments performed at Flare-up Component visits.

4.5 Per Protocol Population

The Per Protocol (PP) Population will include all subjects in the Efficacy Population with no major protocol deviations that may impact the efficacy assessment. Exclusions from the PP Population will be identified prior to database lock. Analyses based on the PP Population will generally be summarized in total. Note that data collected for new unique flare-ups may use each flare-up as the unit of analysis rather than each subject. The PP Population will be a secondary population for analysis of selected efficacy assessments performed at Flare-up Component visits.

5 Treatment Period and Non-Treatment Period

The Treatment Period is defined as the period of days during the Flare-up Component(s) from Flare-up Study Day 1 through the date of completion of the Flare-up Component (ie, Flare-up Study Day 84). The Treatment Period includes all days during Flare-up Components for subjects in the Treated Population.

The Non-Treatment Period is defined as the period of days outside of the Treatment Period. The Non-Treatment Period includes all days in the study for subjects in the Untreated Population and days before, after, or in between Flare-up Components for subjects in the Treated Population.

6 Subject Data

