6.8 Duration of Exposure

Duration of exposure to study drug for each treated flare-up will be calculated from the date of first dose for the flare-up to the date of last dose for the flare-up. Duration of exposure to study drug for each subject will be calculated as the number of days exposed to study drug, ie, the sum of the exposure for each flare-up.

Days of exposure to study drug for flare-ups and subjects will be summarized for the Treated Population with descriptive statistics. Weeks of exposure to study drug will be summarized with counts and percentages of flare-ups in the Treated Population according to the following categories:

- ≤ 2 weeks
- $>2 - 4$ weeks
- $>4 - 6$ weeks

Note that flare-ups with exposure over 42 days (due to windowing) will be included in the last category.

Dose reductions (no dose reductions, any dose reductions) will be summarized with counts and percentages of flare-ups and subjects in the Treated Population.

The number of days after flare-up onset to the date of first dose of study drug for the flare-up will be summarized for the Treated Population with descriptive statistics.

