6.10 Compliance

Compliance to study drug for each treated flare-up will be calculated based on the number of actual capsules taken and the expected number of capsules as specified in the protocol for 42 days of dosing. The number of actual capsules will be calculated as the number of capsules dispensed – the number of capsules returned – the number of capsules lost. For example, a subject who took 10 capsules and was expected to take 42 capsules would be $10/42 = 23.8\%$ compliant.

Percent compliance will be summarized for the Treated Population with descriptive statistics. Categories of percent compliance ($<80\%$, $\geq 80\%$) will be summarized for the Treated Population with counts and percentages of flare-ups.

7 Efficacy Data

Efficacy assessments at Flare-up Component visits will generally be presented in total for the Efficacy Population. The primary efficacy analysis and selected other efficacy analyses will also be presented for the PP Population. Efficacy assessments at Follow-up Component visits will be listed.

Imaging Reads

Imaging data includes results from CT scan, x-ray, MRI, and US. Results will be read and interpreted using two different review processes (Primary Read and Global Read) as described in the study protocol.

The Primary Read review will be performed by two independent musculoskeletal radiologists during the study as images are made available. If there is sufficient agreement between the

independent reviews, both will be used for analysis. If there is insufficient agreement between the independent reviews, an adjudication review will be performed and used for analysis. Imaging procedures performed (yes, yes but not evaluable, no) will be summarized at scheduled visits with counts and percentages of subjects or flare-ups as appropriate.

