8.1 Adverse Events

Adverse events (AEs) will be recorded from the time informed consent is signed through study completion. All AEs will be coded to body system and preferred term using the Medical Dictionary for Regulatory Affairs (MedDRA) Version 17.0. At least possibly related AEs are defined as AEs assessed by the Investigator as possibly, probably, or definitely related to study drug. Adverse events that require Common Terminology Criteria for Adverse Events (CTCAE) grading as indicated on the eCRF are considered to be retinoid-associated AEs.

Adverse events with start date on or after Flare-up Study Day 1 and on or before the date of completion for the Flare-up Component will be attributed to the Treatment Period. Adverse events with start date on or after Study Day 1 that are not attributed to the Treatment Period will be attributed to the Non-Treatment Period.

For the Untreated Population, AEs will be summarized in total (note, these are all Non-Treatment Period AEs). For the Treated Population, AEs will be summarized by period (Non-Treatment Period AEs and Treatment Period AEs) and in total. For the Enrolled Population, AEs will be summarized for the Non-Treatment Period and in total.

The incidence of the following AEs will be summarized with counts and percentages of subjects (overview and also by MedDRA body system and preferred term):

- Any AEs
- Any AEs by maximum severity
- Any AEs at least possibly related to study drug
- Any AEs at least possibly related to study drug by maximum severity
- Any retinoid-associated AEs
- Any retinoid-associated AEs by maximum CTCAE grading
- Any serious adverse events (SAEs)
- Any AEs leading to dose modification or interruption of study drug
- Any AEs leading to discontinuation of study drug
- Any AEs leading to discontinuation of study

Data listings will be provided for (1) all AEs, (2) SAEs, (3) AEs leading to dose modification or interruption of study drug, (4) AEs leading to discontinuation of study drug, and (5) AEs leading to discontinuation of study. Study Day and/or Flare-up Study Day for AE start and stop dates will be included on AE listings as appropriate.

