- TEAEs are AEs with (first dose date of study drug during 202 C) \leq (AE start date) \leq (last dose date of study drug +7 days for all AEs, i.e., non-serious and serious AEs).
 - A chronic TEAE is a TEAE with an onset date during chronic treatment
 - A flare-up TEAE is a TEAE with an onset date during flare-up treatment
- Post-treatment AEs are AEs with a start date $>$ last dose date in Part C + 7 days for All AEs (non-serious and serious AEs).
 - Any AEs
 - Any post treatment AEs
 - Any TEAEs
 - Any TEAEs by maximum severity
 - Any TEAEs at least possibly related to study drug
 - Any TEAEs at least possibly related to study drug by maximum severity
 - Any serious adverse events (SAEs)
 - Any TEAEs leading to dose modification
 - Any TEAEs leading to interruption of study drug
 - Any TEAEs leading to discontinuation of study drug
 - Any TEAEs leading to discontinuation from study

Data listings will be provided for

- All TEAEs
- All post treatment AEs

- SAEs
- SAEs for premature physcal closure and bone safety
- Deaths
- TEAEs leading to dose modification of study drug
- TEAEs leading to interruption of study drug
- TEAEs leading to discontinuation of study drug
- TEAEs leading to discontinuation of study
- AEs ongoing at date of informed consent signed in Part C

Part C Study Day and/or Flare-up Day for AE start and stop dates will be included on AE listings as appropriate.

Adverse event severity will be assessed and reported according to criteria defined in the protocol (mild, moderate, severe). Adverse event causality will also be assessed in terms of relationship to study drug and reported according to criteria described in the protocol (not related, possibly related, probably related, definitely related).

Deaths

Deaths after the first dose of study drug are either on-treatment or post-treatment:

- Deaths on-treatment: deaths occurring after the first dose of study drug and up to 7 days after the last dose of study drug
- Death post-treatment: deaths occurring more than 7 days after the last dose of study drug until 30 days after last dose of study drug

The SAE, including death, reporting period for the non-flare-up-based treatment and the flare-up-based treatment begins at the time of informed consent and continues through study completion (including Part D) + 30 days.

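### Part A's Treatment Period runs to Day 84 although planned dosing is 42 days, so half of it is off drug after a full course and no adverse event table separates the two halves

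*SAP*

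**What the plan says.** The Part A SAP, section 5, sets the Treatment Period as "from Flare-up Study Day 1 through the date of completion of the Flare-up Component (ie, Flare-up Study Day 84". It adds: "The Treatment Period includes all days during Flare-up Components for subjects in the Treated Population". The date of last dose plays no part in the definition.

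The planned course is shorter. Section 2.4 gives "palovarotene 10 mg for 14 days followed by palovarotene 5 mg for 28 days". Section 6.10 bases compliance on the "expected number of capsules as specified in the protocol for 42 days of dosing". Section 6.8 has a top exposure category of more than 4 and up to 6 weeks, with this remark: "Note that flare-ups with exposure over 42 days (due to windowing) will be included in the last category".

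Section 8.1 then uses the period for adverse events. The window opens with the first dose for the flare-up, and events with onset "on or before the date of completion for the Flare-up Component will be attributed to the Treatment Period"; any other event from Study Day 1 onward goes to the Non-Treatment Period. The Treated Population is summarised by these two periods and in total, as counts and percentages of subjects. Section 6.7 applies the same Day 84 cut-off to new-onset medications.

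**The concern.** A column headed Treatment Period will be read as describing subjects on drug. Here the period follows the observation schedule of the Flare-up Component, not dosing. Events that begin up to six weeks after the planned last dose sit beside events on drug, under one label. Subjects who stop early are affected most, because the period does not end with their last dose.

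What is at stake is how the Part A safety tables are interpreted. A reader cannot tell from them how many subjects had an event while taking palovarotene and how many had one only afterwards. The off-drug days of treated subjects that come closest in time to dosing are also missing from the non-treatment column.

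**Working it through.** **Inputs (all from the Part A SAP unless stated)**

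- Planned dosing: 14 days then 28 days (section 2.4).
- Treatment Period: Flare-up Study Day 1 to Day 84 (section 5).
- Flare-up Component visits: last at Week 12, with windows of ±3 days (section 2.3).
- Part B planned flare-up dosing: 28 days then 56 days (Part B SAP, section 2.4).

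**The plan's own figures**

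- Dosing: 14 + 28 = 42 days, which agrees with the 42 days in sections 6.8 and 6.10.
- Period length: 84 − 1 + 1 = 84 days = 12 × 7, which agrees with the Week 12 visit.

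**Off-drug share of the Treatment Period**, calculated as (period length − day of last dose) / period length

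- Full course: (84 − 42)/84 = 42/84 = 50.0%.
- Completion moved by ±3 days: (81 − 42)/81 = 48.1% to (87 − 42)/87 = 51.7%.
- Last dose moved by ±3 days: (84 − 45)/84 = 46.4% to (84 − 39)/84 = 53.6%.
- Last dose on Day 28: (84 − 28)/84 = 66.7%.
- Last dose on Day 14: (84 − 14)/84 = 83.3%.

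The early-stopping figures assume that the subject stays in the Flare-up Component to Day 84.

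**With a post-dose lag counted as on drug**

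- A 7-day lag gives 42 + 7 = 49 on-drug days and 84 − 49 = 35 post-dose days, or 35/84 = 41.7% of the present period.

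**Comparison with Part B**

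- Planned flare-up dosing is 28 + 56 = 84 days, so 84 − 84 = 0 days of an 84-day period are off drug. Part B SAP section 7.1 ends its flare-up period when flare-up treatment is completed. Day 84 is thus the planned end of dosing in Part B, but falls 42 days after the planned last dose in Part A.

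**Direction of the effect on the tables**

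Section 8.1 reports percentages of subjects. Adding Days 43–84 to the treatment column can only leave the number of subjects with an event unchanged or raise it. Removing those days from the non-treatment column can only leave its number unchanged or lower it. The size of either change depends on event rates that the SAP does not give.

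**The case against.** The best defence is that the rule is explicit and applied consistently. Section 5 says that the period covers the whole Flare-up Component, and sections 6.7 and 8.1 follow it. The period matches the scheduled safety follow-up, which continues to Week 12 for laboratory tests, vital signs and weight. Counting some post-dose time is ordinary practice. All of this stands: the problem is a misleading label and a missing split, not a contradiction in the attribution rule. The SAP gives no reason, however, for a 42-day tail.

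There is also mitigation. Section 8.1 separately tabulates events judged at least possibly related and events leading to dose modification, interruption or discontinuation of study drug. The listings carry Flare-up Study Day, so the split could be made by hand in a study of about 40 enrolled subjects. That also stands, but relatedness is an open-label judgement and not timing, and a listing is not a summary.

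Three stronger readings are tempting and are not supported.

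- A reader might infer that Treatment versus Non-Treatment Period is Part A's principal safety comparison and that a drug effect is diluted by a calculable factor. The SAP names no such comparison and plans no rates or rate ratios, and any dilution figure would need event rates that it does not contain.
- A reader might take 50% of the days to mean 50% of the events or of the affected subjects. It is a share of time only.
- A reader might infer that Part C already applies a 7-day window after each flare-up, so that Part A breaks a study-wide rule. Part C SAP section 7.1 anchors its lag to the "last dose date in Part C + 7 days for All AEs", ends its flare-up period at completion of flare-up treatment with no lag, and elsewhere calls all events from consent treatment emergent. It is a precedent for the length of a lag, not a standard that Part A violates.

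**Conclusion.** The point holds as a matter of labelling and tabulation. In Part A, 42 of the 84 Treatment Period days (50%) are off drug after a planned course, about 46% to 54% when visit windows are allowed for, and more after early stopping. Adverse events from those days are reported only as Treatment Period events, and no table shows their timing relative to last dose.

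The 50% rests on a completed 42-day course and a Component that ends on Day 84. The effect on the reported percentages has a known direction within each column but no size that can be derived from the SAP. The primary efficacy analysis, no new heterotopic ossification at Week 12, does not use this period. This is a cheap improvement to the safety reporting and does not invalidate the planned analysis.

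**What to change.** In Part A SAP section 8.1, divide the Treatment Period adverse event column by the actual last dose of each flare-up:

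- **On drug:** Flare-up Study Day 1 through last dose plus a lag fixed in the SAP, for example 7 days, similar in length to the lag that Part C applies after the last dose in Part C.
- **Post-dose follow-up:** the next day through completion of the Flare-up Component.
- **Combined:** the two together, which is the column now planned. A subject with events in both parts counts once here, so the two percentages need not add up to the combined one.

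Section 5 should define the two sub-periods, and statements about events on treatment should rest on the on-drug column. The same split for new-onset medications in section 6.7 is optional.

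The cost is a few lines of SAP text and additional columns derived from dose and event dates already collected. Nothing planned is lost, because the combined column stays. The small downside is fewer events in each column. The change concerns reporting only and touches no dosing or clinical rule.
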